2.3 BENEFIT/RISK ASSESSMENT

Within the context of this Phase 4 study, a favorable risk-benefit assessment for the Investigational medicinal products (IMPs) (Toujeo and Tresiba) is already well established. The use of both drugs in this study is according to the approved National Product Label.

With the exception of minimal laboratory assessments at screening, the study procedures (including the use of CGM) are consistent with the standard-of-care for these patients. The risks arising from the minimal blood sampling required by the protocol and also for the CGM sensor placement (limited to infrequent occurrence of local skin reaction) are low.

Potential benefits to participants arise from the opportunity for treatment optimization and the availability of the CGM data following unblinding.

More detailed information about the known and expected benefits and risks and reasonably expected AEs of Toujeo and Tresiba may be found in the Summary of Product Characteristics.

3 OBJECTIVES AND ENDPOINTS

Table 1 - Objectives and endpoints

Objectives	Endpoints
Primary	
To demonstrate the noninferiority of insulin glargine 300 U/mL in comparison to insulin degludec 100 U/mL on glycemic control and variability in participants with diabetes mellitus	Percent time in glucose range of ≥70 to ≤180 mg/dL (≥3.9 to ≤10 mmol/L) at Week 12, obtained using continuous glucose monitoring (CGM)
Secondary	
To evaluate the glycemic control and variability parameters in each treatment group at Week 12 using CGM	At Week 12, the following endpoints will be assessed: Glucose total CV
	 Glucose within-day and between-day CV
	Other secondary endpoints:
	 Change from baseline to Week 12 in HbA1c Change from baseline to Week 12 in central lab FPG
	 Percent time and mean hours per day with glucose<70mg/dL (on all time and during the night [00:00 to 05:59])
	 Percent time and mean hours per day with glucose>180mg/dL
To evaluate the safety of insulin glargine 300 U/mL in comparison to insulin degludec 100 U/mL	Number of participants with adverse events (see Section 8.3)
	Number of participants with at least one hypoglycemic event from baseline to Week 12
	Number of hypoglycemic events per participant year from baseline to Week 12
Tertiary/exploratory	
To explore the glycemic control and variability parameters in each treatment group at Week 12 using CGM	Mean hours per day in the glucose range of ≥70 to ≤180 mg/dL (≥3.9 to ≤10 mmol/L)
	Percent time and mean hours per day in the glucose range of \geq 70 to \leq 140 mg/dL (\geq 3.9 to \leq 7.8 mmol/L) (on all-time and during the night [00:00 to 05:59])
	Nocturnal percent time in glucose range of ≥70 to ≤180 mg/dL (≥3.9 to ≤10 mmol/L) at Week 12, obtained using CGM
	Percent time and mean hours per day with glucose: <54 mg/dL, (on all time and during the night [00:00 to 05:59])
	Percent time with glucose <70 mg/dL within the 12 hours after basal insulin injection
	Percent time and mean hours per day with glucose >250 mg/dL
	Mean glucose profile over 24-hour period 24h-AUC

Objectives	Endpoints
	Daily insulin doses (total daily insulin, total basal insulin, total bolus insulin, ratio of basal to bolus insulin dose) in units and U/kg body weight
	Change from baseline to week 12 in patient-reported outcomes (treatment satisfaction, sleep quality and quantity, and productivity)
	7-point SMPG profiles (preprandial and 2-hour postprandial plasma glucose at breakfast, lunch dinner and bedtime) at Week 12 and change in 7-point SMPG profiles from baseline to Week 12

3.1 APPROPRIATENESS OF MEASUREMENTS

The primary efficacy endpoint is based on the CGM recording to be collected during Weeks 10-12, representing the last 3 weeks of the 12 week IMP (either Toujeo or Tresiba) treatment period by which time stable doses are anticipated (ie, IMP titration phase expected to be up to Week 8, see Section 6.6.1.2).

Secondary analyses will be performed to evaluate the therapeutic feature of a flatter and longer duration of Toujeo compared to Tresiba over at least 24 hours, which should result in more sustained glycemic control, and less hypoglycemia during nighttime. The assessment will be measured by the secondary and exploratory endpoints of: the incidence rate of nocturnal documented symptomatic hypoglycemia, and the variability analyses of CGM profiles.

The CGM system allows frequent glucose measurements (every 5 minutes) and the ability to analyze glucose distributions in real time (14, 15). Use of this approach in a clinical study provides the opportunity to better understand glucose metabolism associated with the study IMP. This approach has been employed previously in studies of the efficacy of long-acting insulins in patients with diabetes.

Mealtime insulin titration will also be implemented to achieve the postprandial SMPG targets. Thus, the glycemic control measured by laboratory HbA1c and FPG at Week 12 is expected to be similar between the two treatments.

Frequent SMPG assessment values will be used to guide the insulin dose titration and to support the analyses of 7-point SMPG profile and hypoglycemia reports. At Visits 6, 14, 15 and 18 the SMPG data will be uploaded from the glucometer onto the site computer so that the Investigator and study staff are able to check the patient's comprehension and compliance with dose adjustments and diary completion and to identify potential non-reported episodes of hypoglycemia. Safety analyses include a thorough hypoglycemia analysis on incidence rate, proportion of patients with hypoglycemia and the diurnal distribution of hypoglycemia. These analyses will be performed based on the SMPG and the hypoglycemic events reported by the patients. Patients will be instructed to measure SMPG whenever they feel hypoglycemic. This aims to detect and confirm as many hypoglycemic episodes as possible.

Sponsor will implement the monitoring of titration for both basal and meal time insulins to ensure optimal dosing.

Patient-Reported Outcomes (PRO):

Patients will complete self-reported questionnaires at designated time points in the study:

The Diabetes Treatment Satisfaction Questionnaire Status and Change Versions (DTSQs and DTSQc, respectively) (16, 17) will be used to evaluate patient satisfaction with treatment and patient perception of blood glucose control over a several-week period.

The MOS Sleep questionnaire will be used to measure patient perception on key aspects of sleep (18). The WPAI will be used to measure absenteeism, presenteeism and work productivity (19).

4 STUDY DESIGN

4.1 OVERALL DESIGN

This is a multicenter, randomized, active-controlled, parallel-group, 12-week open-label study. The study consists of a 1- or 2-week screening period, followed by a 4-week run-in period, and a 12-week randomized treatment period.

During the first 2 weeks of the run-in period (Weeks -4 and -3), patients will undergo treatment stabilization of their current basal and mealtime insulin treatment, and will be trained and tested on how to perform study-related procedures. During the (-)3 – (-)1 weeks of run-in, patients will wear a CGM device, blinded both to patients and Investigators. This will be the baseline CGM period, when during 20 consecutive days, a minimum of (10 days, not necessarily consecutive) of useable CGM data must be generated, to be eligible for randomization.

Patients satisfying the study inclusion/exclusion criteria (including CGM performance requirements) will be randomized in a 1:1 ratio to morning injections of either Toujeo or Tresiba, which will replace the patient's current basal insulin.

An interactive response technology (IRT) will be configured and randomization will be stratified by HbA1c at screening (<8.0%; $\ge8.0\%$).

During the randomized treatment period, CGM data (blinded to both patients and Investigators) will be collected during Weeks 9-12 during 20 consecutive days.

The basal insulin injection will be once daily in the morning, defined as the time period between waking up and breakfast. The injection time will be discussed between the Investigators and patients at randomization and should be kept consistent at the same time each day.

During the entire study starting after the screening period, patients will perform SMPG as specified in the study flow chart. The SMPG readings will be used to guide insulin dose titration for optimal glycemic control.

Appropriate dose titration of basal and mealtime insulin will be implemented as described in the dose regimen section.

At the end of the study, the patients will be followed-up from 2 to 4 days after last IMP dose to collect posttreatment safety information.

4.2 SCIENTIFIC RATIONALE FOR STUDY DESIGN

The fluctuations in blood glucose, regular short-duration periods of hyperglycemia and hypoglycemia, which are not detected by the measurements of HbA1c, may possibly contribute to vascular pathological processes and diabetic complications. This association may be independent of average glucose exposure expressed by HbA1c. This hypothesis remains controversial, but stems from the observation that intensive (versus standard) glucose control in the DCCT was associated with reduced risk for retinopathy after correcting for HbA1c (4). Supportive observations report that the coefficient of variation of FPG independently predicted mortality in T2DM (5). Potential mechanisms that might link oscillating blood glucose with vascular pathology include oxidative stress and inflammatory processes, with enhanced apoptosis of vascular endothelial cells (6).

This is a randomized, active-controlled, 12-week open-label study to compare the efficacy of Toujeo with Tresiba using CGM glucose profiles, sampling ambulatory glucose level every 5-minutes over a 20-day period at Week 12. The CGM during study period will be blinded to both the Investigators and patients.

Eligible patients will be randomized to either Toujeo or Tresiba, both given once-daily by SC injection in the morning. Patients allocated to Toujeo or Tresiba groups will switch from their previous basal insulin. During 4 weeks of the run-in period, patients will be required to titrate their basal and mealtime insulin to optimize the fasting and 2-hour postprandial self-monitoring of plasma glucose (SMPG) targets. The baseline CGM will be performed during the last 3 weeks of run-in.

The primary objective of the study is to explore the percent of time in target CGM glucose range of 70-180 mg/dL with Toujeo versus Tresiba treatment at 12 weeks of treatment. In addition, all hypoglycemia incidence and distribution (24 hours and nocturnal) will be analyzed according to the American Diabetes Association (ADA) classification (severe, documented symptomatic, asymptomatic, probable and relative) (20). Glucose stability and variability will be assessed between and within each group via measurements of glucose CV.

A relatively homogenous patient population will be selected, reducing potential confounding effects, so that the true differences in the therapeutic effects of Toujeo versus Tresiba can be assessed. The study population includes patients 18-70 years of age with T1DM, on a basal plus mealtime insulin regimen for at least one year, and HbA1c level \geq 7% and <10%. Patients must be on a stable dose of basal/bolus insulin regimen for 30 days before screening.

Repeat assessments of selected PROs will be performed during the study as the exploratory analyses (including patient satisfaction with treatment and patient perception of blood glucose control assessed by Diabetes Treatment Satisfaction Questionnaire [status and change version - DTSQs and DTSQc], MOS Sleep Scale to measure key aspects of sleep and the Work Productivity and Activity Impairment Questionnaire [WPAI]- Diabetes; assessing the impairment on daily work and activities due to diabetes) in order to reveal any potential link between improvement in continues glucose profile and patient well-being.

4.3 JUSTIFICATION FOR DOSE

During the first 2 weeks of the run-in period (Weeks -4 and -3), patients will be required to titrate their basal and mealtime insulin to stabilize the fasting and 2-hour postprandial SMPG targets of \geq 70 to \leq 100 mg/dL (\geq 3.9 to \leq 5.6 mmol/L) while avoiding hypoglycemia episodes.

At randomization, the initiation doses of Toujeo and Tresiba will be the patient's current doses of their basal insulin on a unit-to-unit basis.

Dose adjustments will be based on a median of fasting SMPG values from the last 3 days, which will include the value measured on the day of titration, measured by the patient using glucometers and accessories supplied by the Sponsor. Appropriate dose titration of IMP and mealtime insulin is expected to be up to Week 8.

During the randomized treatment period, IMP injection will be administered once daily each morning at the same time.

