- Route of administration: subcutaneous.
- Dose regimen: The injection time and frequency of rapid-acting (mealtime) insulin will be at the Investigator's discretion, in accordance with the National Product Label. During the study, the doses of the mealtime insulin analog should be actively titrated to achieve and maintain the 2 hour postprandial SMPG in the range ≥130 to ≤180 mg/dL (≥7.2 to <10 mmol/L) while avoiding hypoglycemia. Dose adjustment of mealtime insulin can be based on a pattern of post-meal SMPG data from the prior 3 days (simple titration) OR the carbohydrate content of the meal. Sponsor will ensure adequate monitoring of mealtime insulin titration.

Simple titration: Titration of mealtime insulin based on a pattern of post-meal glucose median <130 />180 mg/dL in the prior 3 days using the table below.

Mealtime dose of Insulin	Pattern of Postprandial Plasma Glucose values <130 mg/dL ^a	Postprandial Plasma Glucose values >180 mg/dL ^a				
≤10 units	Decrease dose by 1 unit	Increase dose by 1 unit				
≥11-19 units	Decrease dose by 2 units	Increase dose by 2 units				
≥20 units	Decrease dose by 3 units	Increase dose by 3 units				

a If more than half of the mealtime plasma glucose (2-hours postprandial plasma glucose) values for the week were above target.

OR

Carb counting: (insulin-to-carbohydrate ratio) group.

Starting recommendation 1 unit to 15 grams carbs

Consider calculating insulin to carb (I:C) ratio = 500/total daily dose (TDD) of insulin.

Mealtime dose of Insulin	Pattern of Postprandial Plasma Glucose values <130 mg/dL ^a	Pattern of Postprandial Plasma Glucose values >180 mg/dL ^a						
1 unit/20 g	Decrease to 1 unit/25 g	Increase to 1 unit/15 g						
1 unit/15 g	Decrease to 1 unit/20 g	Increase to 1 unit/10 g						
1 unit/10 g	Decrease to 1 unit/15 g	Increase to 2 unit/15 g						
2 unit/15 g	Decrease to 1 unit/10 g	Increase to 3 unit/15 g						
3 unit/15 g	Decrease to 2 unit/15 g	Increase to 4 unit/15 g						

a If more than half of the mealtime plasma glucose values for the prior 3 days were above target.

Statistical considerations:

Sample size

The sample size calculation is based on the percent time spent in glucose range of \geq 70 to \leq 180 mg/dL (\geq 3.9 to \leq 10 mmol/L) at Week 12, assessed from CGM measurements obtained from Weeks 10 to 12.

For this criterion of percent time in range, there is no predefined non-inferiority margin. A relative non-inferiority margin of 10% is considered.

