6.6 DOSE MODIFICATION

Note: During the first 2 weeks of the run-in period, patients will be required to titrate their basal and mealtime insulin to stabilize the fasting and 2-hour postprandial self-monitoring of plasma glucose (SMPG) targets.

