6.6.1 Basal insulin

The patient's basal insulin dose will be titrated with the objective of reaching a target fasting SMPG of \geq 70 to <100 mg/dL (\geq 3.9 to <5.6 mmol/L) while avoiding hypoglycemia episodes (ie, this is identical to the algorithm to be used for IMP see Section 6.6.1.2). Note: fasting SMPG should be taken within 30 minutes prior to injection of current basal insulin (if applicable) and before breakfast.

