6.6.1.2 Dose adjustment

6.6.1.2.1 Dose adjustments based on target fasting SMPG

During the titration phase (expected to be up to Week 8), doses of IMP (either Toujeo or Tresiba) will be titrated to achieve glycemic targets without hypoglycemia according to the algorithm outlined in Table 3.

The IMP dose will be titrated at least weekly (but no more often than every 3 days), until the patient reaches a target fasting SMPG of ≥70 to <100 mg/dL (≥3.9 to <5.6 mmol/L) while avoiding hypoglycemia episodes.

Dose adjustments will be based on a median of fasting SMPG values from the last 3 days, which will include the value measured on the day of titration, measured by the patient using glucometers and accessories supplied by the Sponsor.

Table 3 - Basal insulin dose adjustments

Median ^a fasting pre-breakfast SMPG values (last 3 days)	Basal insulin dose adjustments (U/day) ^b
≥140 mg/dL (≥ 7.8 mmol/L)	+4 units
≥100 and < 140 mg/dL (≥5.6 and <7.8 mmol/L)	+2 units
≥70 and <100 mg/dL (≥3.9 and <5.6 mmol/L)	No change
≥56 and <70 mg/dL (≥3.1 and <3.9 mmol/L)	-2 units
<56 mg/dL (<3.1 mmol/L) or occurrence of 2 (or more) symptomatic hypoglycemic episodes or 1 severe hypoglycemic episode	 -4 units or at the discretion of the Investigator or medically qualified designee

Abbreviation: SMPG = self-monitoring of plasma glucose

a Median refers to intermediate SMPG value (the value between the lowest and the highest SMPG values when the values are ranked in a growing order).

b Prior to additional basal insulin titration, mealtime insulin should be titrated to achieve a bedtime and pre-breakfast glucose delta <50 mg/dL, if so considered helpful by the Investigator.

Regular SMPG is very important in order to achieve blood glucose targets. It is necessary to perform daily fasting/pre-breakfast SMPG and postprandial measurements (Section 8.1.4) to support the titration. More frequent SMPG at other time-point may be needed at the Investigator's discretion.

Patients will be familiarized with the adjustment schedule so that they will be able to monitor the dose adjustment with the assistance of the Investigator or medically qualified designee. During the study, contacts between the Investigator and patient are scheduled to assess the response to treatment and to decide on dose adjustment. During these visits, patients will report their SMPG data, insulin doses and hypoglycemia to the study site.

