6.6.2 Mealtime insulin

From Visit 2, the injection time (in relation to the meal intake) and frequency of mealtime insulin (ie, rapid-acting insulins: insulin glulisine, insulin lispro or insulin aspart) will be at the Investigator's discretion, in accordance with the relevant National Product Labels.

The dose of the mealtime insulin analogs will be actively titrated to achieve a target of 2-hour postprandial plasma glucose. The dose adjustment regimen can be titrated based on a pattern of postprandial plasma glucose results of SMPG from the prior 3 days (simple titration based on a pattern of post-meal glucose median <130/>180 mg/dL) or based on the carbohydrate content of the meal (carb counting).

The titration goal is a 2-hour postprandial SMPG in the range of ≥ 130 to ≤ 180 mg/dL (≥ 7.2 to ≤ 10 mmol/L) while avoiding hypoglycemia. For the purpose of this protocol, 2-hour postprandial is defined as 2 hours after the start of the meal.

Dose of mealtime insulin will be recorded in the patient's diary and eCRF. **Note:** It is essential that this data is captured on the day of randomization.

While basal insulin doses are increased, mealtime insulin doses may be reduced to avoid daytime hypoglycemia as deemed appropriate by the Investigator.

Appropriate adjustment in mealtime insulin will continue throughout the study (Visits 2 to 18).

The two regimens are described in Table 4 and Table 5.

Table 4 - Rapid-acting insulin dose adjustment

Mealtime dose of insulin	Pattern of postprandial plasma glucose values <130 mg/dL ^a	Postprandial plasma glucose values >180 mg/dL ^a
≤10 units	Decrease dose by 1 unit	Increase dose by 1 unit
≥11-19 units	Decrease dose by 2 units	Increase dose by 2 units
≥20 units	Decrease dose by 3 units	Increase dose by 3 units

a If more than half of the mealtime plasma glucose (2-hour postprandial plasma) values for the week were above target.

Table 5 - Carb counting: insulin-to-carbohydrate ratio

Mealtime dose of insulin	Pattern of postprandial plasma glucose values <130 mg/dL ^a	Pattern of postprandial plasma glucose values >180 mg/dL ^a Increase to 1 unit/15 g	
1 unit/20 g	Decrease to 1 unit/25 g		
1 unit/15 g	Decrease to 1 unit/20 g	Increase to 1 unit/10 g	
1 unit/10 g	Decrease to 1 unit/15 g	Increase to 2 unit/15 g	
2 unit/15 g	Decrease to 1 unit/10 g	Increase to 3 unit/15 g	
3 unit/15 g	Decrease to 2 unit/15 g	Increase to 4 unit/15 g	

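### The mealtime insulin rules disagree with themselves in three places: the run-in postprandial target, the footnote on the dose-decrease column, and the look-back for simple titration

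*Protocol*

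**What the plan says.** **Run-in target.** Protocol section 4.3, on Weeks -4 and -3, says "patients will be required to titrate their basal and mealtime insulin to stabilize the fasting and 2-hour postprandial SMPG targets of" 70 to 100 mg/dL, "while avoiding hypoglycemia episodes". Section 6.6 repeats the instruction to "stabilize the fasting and 2-hour postprandial self-monitoring of plasma glucose (SMPG) targets" but gives no range. Section 6.6.1 links 70 to <100 mg/dL to fasting glucose: the "basal insulin dose will be titrated with the objective of reaching a target fasting SMPG of" that range. Section 6.6.1.2.1 does the same for the study drug: "until the patient reaches a target fasting SMPG of ≥70 to <100 mg/dL".

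**Mealtime target.** Section 6.6.2 states: "The titration goal is a 2-hour postprandial SMPG in the range of ≥ 130 to ≤ 180 mg/dL". Its rules start at Visit 2 (Week -4) and run to Visit 18. The synopsis agrees, asking sites to achieve and "maintain the 2 hour postprandial SMPG in the range ≥130 to ≤180 mg/dL".

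**Tables 4 and 5.** The decrease column is headed by a pattern of postprandial values <130 mg/dL and the increase column by values >180 mg/dL. Both headings carry footnote a. The only condition in that footnote is that more than half of the values were above target. The two synopsis tables repeat this.

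**Look-back.** For simple titration, the text of section 6.6.2 and of the synopsis uses the median of the prior 3 days. The footnote to Table 4 and its synopsis copy use the week's values. The carb-counting footnote (Table 5) uses 3 days.

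**The concern.** Sites titrate rapid-acting insulin from these numbers in patients with type 1 diabetes. A site that follows section 4.3 literally aims for postprandial values that the titration tables treat as a reason to cut the dose. A site that follows footnote a literally withholds a reduction that a low pattern calls for. Two sites that choose different look-back periods can reach different decisions from the same diary. The section 4.3 conflict ends before randomization. The footnote and look-back conflicts continue, because mealtime titration runs to Visit 18.

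**Working it through.** The plan gives no computed figure on this point, so the check compares the statements with each other and then counts cases.

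**1. Run-in target.**

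| Source | Period | 2-hour postprandial target (mg/dL) |
|---|---|---|
| Section 4.3 | Weeks -4 and -3 | 70 to 100 |
| Section 6.6.2 | Visits 2 to 18, so from Week -4 | 130 to 180 |
| Synopsis | During the study | 130 to 180 |

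The gap is 130 − 100 = 30 mg/dL, so no value meets both targets. Every value from 70 to 100 is below 130 and falls under the decrease heading. Whether the upper limit in section 4.3 is ≤100 or <100 makes no difference.

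**2. Footnote on the decrease column.** Call each 2-hour value low (<130), in range (130 to 180) or high (>180). Assume that above target means high, and that the footnote refers to the same 2-hour values as the column heading.

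*Table 5 (prior 3 days, three readings).*
- There are 3³ = 27 patterns.
- The heading needs at least 2 of 3 low: 1 pattern with three low, plus 3 × 2 = 6 with exactly two low, total 7.
- The footnote needs at least 2 of 3 high. No pattern can meet both, so the count is 0 of 7.

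*Table 4 (one reading a day for a given meal, over 7 days).*
- There are 3⁷ = 2187 patterns.
- A low 3-day median needs at least 2 of the last 3 low: 3⁴ × 7 = 81 × 7 = 567 patterns.
- The footnote also needs at least 4 of 7 high. With at least two of the last three low, at most one of them is high, which leaves two routes:
  - all 4 earlier days high, with any of the 7 qualifying endings: 1 × 7 = 7;
  - exactly 3 of the 4 earlier days high (4 × 2 = 8 patterns), with exactly one of the last three high (3 endings): 8 × 3 = 24.
- Total 7 + 24 = 31, and 31/567 = 5.5%.

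A week in which every reading is 110 mg/dL has 0 of 7 high, so the literal footnote gives no decrease, although this is plainly a case for one.

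**3. Look-back.** Take the illustrative daily values 150, 150, 150, 150, 190, 190, 190 mg/dL.
- 3-day rule: the median is 190, above 180, so increase.
- Weekly rule: 3 of 7 are above 180, not more than half, so no increase.

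The two periods therefore give different decisions even in the increase column, where the direction of the footnote is right.

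**The case against.** The strongest reply is that a clinician would not be misled. Section 4.3 is a rationale section that names two targets and prints only the fasting one. Section 4.2 and section 6.6 give the run-in instruction without that range, and the dosing sections are clear. In the tables, the column headings and cell entries fix the direction, so footnote a is naturally read as more than half of values out of range in the direction of the column. A weekly check alongside a 3-day median is a possible reading, since titration contacts are weekly. Section 6.6.1.2.2 lets mealtime doses be reduced at any time for hypoglycemia, section 6.6.2 lets them be reduced to avoid it while basal doses rise, and section 6.6.3 places titration under sponsor monitoring. Finally, the pattern counts assume one reading per meal per day, which the protocol does not require, and weight all patterns equally.

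Most of this stands, and it is why the point is minor. The counts show what the wording permits; they do not estimate how often anything would happen. But inferable intent does not make the text consistent, and the tables and footnotes are themselves in the operative dosing section. Applying the weekly and 3-day conditions together is what produces the 31 of 567 result, so that reading does not rescue the decrease column. The decrease column is meant to act on any pattern below 130 mg/dL, well before the 70 mg/dL hypoglycemia threshold, so permission to reduce for hypoglycemia is not a full substitute. The supervision manual is not among the documents and cannot be assumed to settle the matter.

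**Conclusion.** All three inconsistencies are in the current protocol text, and the point holds as minor. The postprandial targets in sections 4.3 and 6.6.2 are 30 mg/dL apart for the same run-in weeks. The misdirected footnote appears in four places. Read literally, it leaves 0 qualifying patterns for a Table 5 decrease and 31 of 567 for a Table 4 decrease. The look-back is 3 versus 7 days, in simple titration only. The pattern counts rest on above target meaning above 180 mg/dL, on the footnote and heading referring to the same 2-hour values, and, for Table 4, on one reading a day per meal. Both arms follow the same rules. No bias is shown, and no effect on time in range can be computed from the documents.

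**What to change.** - **Section 4.3:** limit 70 to <100 mg/dL to fasting SMPG, and state 130 to 180 mg/dL for 2-hour postprandial SMPG, as in section 6.6.2.
- **Tables 4 and 5 and their synopsis copies:** give the decrease column its own footnote, requiring more than half of the values to be below 130 mg/dL. Keep the existing above-target footnote for the increase column only.
- **Table 4 footnote and its synopsis copy:** replace the weekly period with the prior 3 days, to match the text and the carb-counting rule.
- **Sites:** send a short clarification letter.

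The cost is these wording changes and the letter. No visits, procedures or patients are added.
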